### 1. Introduction

Advances in mobile health (mHealth) not only allow for accessible and cost-effective intervention, but also offer novel opportunities for delivering personalized and adaptive interventions in real-time, in the real world. Analogous to personalized medicine, just-in-time adaptive interventions (JITAIs) are an emerging approach that operationalizes the personalization of the real time selection, and delivery of intervention strategies, based on real time data collection. This approach has had large clinical impact in managing cardiovascular disease and diabetes and JITAIs have been developed and evaluated for a wide range of behavioral health issues (e.g., mental illness, smoking cessation).

mHealth interventions offer novel opportunities for delivering JITAIs based on real-time data collection to reduce substance use. Such approaches are lacking for substance use (SU; alcohol, cannabis, opioids) among emerging adults (EAs), which is critical because they are avid digital adopters. Also, SU is initiated in adolescence, reaches peak prevalence during emerging adulthood, and is associated with morbidity and mortality (i.e., injury, violence, suicide, overdose).

Critical challenges exist to developing evidenced-based, personalized, real-time mHealth interventions that can address youth SU. 1) Existing mobile interventions for SU primarily focus on adults, and/or individuals with substance use disorders (SUDs;<10% of EAs), missing youth and young adults with risky use. 2) Adequate engagement with mHealth tools is necessary for success; yet attrition in mHealth interventions is common, including those targeting SU. 3) There is high heterogeneity in response to mobile interventions targeting EA SU; many EAs do not benefit sufficiently from mHealth alone and require some level of human (e.g., coach) support to facilitate change. Addressing these challenges requires multidisciplinary effort, involving clinicians, engineers, methodologists, decision scientists, health economists, computer scientists and human-computer interaction (HCI) specialists.

Current mHealth substance use interventions, including JITAIs, focus primarily on treatment seeking samples with substance use disorders (SUDs) and/or adults, which is a missed opportunity to intervene earlier in substance use trajectories by focusing on broader samples of non-treatment seeking EAs with risky use. Despite promising emerging data, evidence-based JITAI for cannabis use among EAs are lacking. Reducing cannabis and other drug use among EAs could have a major public health impact by preventing health consequences (e.g., injury), development of SUDs, and associated risk behaviors (e.g., dugged driving). To address

this gap, consistent with the Multi-Phase Optimization Strategy (MOST) approach, we conducted a series of pilot studies to inform the proposed JITAI. First, we developed an ecological momentary assessment app called SARA, which integrates gamification via an aquarium with scalable engagement strategies. A pilot micro-randomized trial (MRT) of SARA among 74 EAs with substance use showed excellent acceptability and 30-day engagement ( $M$  daily surveys=18.1,  $SD$ =9.2) despite much lower financial incentives ( $M$ =\$6.24,  $SD$ =\$3.83, range: \$1-13) compared to previous daily self-report studies; further, inspirational messages increased daily survey completion. Second, we integrated feedback from SARA into a prototype JITAI, and obtained acceptability data among 39 substance-using EAs, establishing a blueprint for future refinement of the MiSARA JITAI.

## 2. Objectives

Given that cannabis use peaks among EAs and changing norms and policies have led to increases in availability and reductions in perceived risks of cannabis use, we aim to develop a JITAI to reduce cannabis use among non-treatment seeking EAs who use cannabis thrice weekly. Using a transdisciplinary approach, the JITAI will integrate empirically based intervention strategies for reducing substance use (e.g., motivational interviewing and mindfulness) with engagement strategies grounded in areas such as basic psychology, human computer interaction (HCI), and marketing, which are necessary for efficacious mHealth interventions.

In this study, we will innovatively build on the results from our prior MRT optimizing app engagement (SARA) and prior feasibility/acceptability pilot of a prototype JITAI (MiSARA JITAI). In Aim 1, based on participant feedback, we will refine the MiSARA JITAI app environment to improve engagement by increased interactivity and personalization to maintain novelty throughout the intervention period. Then, we will test the feasibility, acceptability, and preliminary efficacy of a person specific JITAI called MiWaves for reducing cannabis use in this critically important EA population.

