**Aim 1: Refine the MiSARA JITAI to reduce cannabis use among EAs.**

**Aim 2: Conduct a pilot trial to test the feasibility and acceptability of MiWaves, a 2nd generation MiSARA JITAI with continually optimized population-based decision rules.**

The achievement of the proposed aims addresses a significant public health problem, namely the increases in cannabis use among EAs. The innovation is grounded in the development of a real-time, real-world, personalized, and scalable intervention approach to reduce substance use among EAs. This work is highly innovative since, despite promising results, evidence based JITAIs for cannabis use among EAs are lacking. Reducing cannabis and other drug use among EAs could have a major public health impact by preventing adverse health consequences (e.g., injury), development of SUD, and associated risky behaviors (i.e., drugged driving).

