## 4. Methods

**Aim 1: Refine the MiSARA JITAI to reduce cannabis use among EAs.**

This aim does not include human subjects. Instead, it includes the development of (a) therapeutic content and (b) engaging content and human computer interfaces. Using a participatory action approach, we will integrate EA feedback from our formative studies with consultation from a new EA advisory board to create the MiWaves JITAI app.

Refinements may include:

- increased interactivity and personalization of the app,
- integration of data into personalized feedback graphs,
- personalization of messages based on behavioral trends to increase novelty, and
- archiving intervention content in a virtual toolbox and creating 'on-demand' pulls for additional messages.

A collection of empirically- and theoretically-grounded therapeutic content will be identified and developed by multiple intervention experts to maximize engagement. Therapeutic content will harness a variety of mediums and may include: a) messages (targeting goals, strengths; benefits to change, tools to address motives); b) brief videos (e.g., focusing on goal setting and attainment, protective behavioral strategies, safe driving, overdose prevention, other strategies); and c) life-insights visualizations -- feedback capitalizing on Ecological Momentary Assessments (EMAs) to visually integrate information about behaviors, risk and protective factors. Intervention content will be reviewed by an advisory board of EAs and selected based on fit with evidenced-based intervention content (e.g., motivational interviewing) and appropriateness (e.g., no images glamourizing use, offensive jokes). Intervention experts on our team will collaborate with engagement experts, machine-learning experts and HCI experts to further develop and refine various types of visualizations to specifically address cannabis use related risk.

**Aim 2: Conduct a pilot trial to test the feasibility and acceptability of MiWaves, a 2nd generation JITAI with continually optimized population-based decision rules.**

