This aim includes human subjects. Specifically, it includes the following: a) conduct EA enrollment and obtain feedback, and b) software refinement. Based on prior work and Aim 1 feedback from EA advisors, the MiWaves app will be iteratively refined among a total of 150 EAs (ages 18-25). Participants who report cannabis use three or more times per week in the past month (see Inclusion/Exclusion criteria below for more information) will be recruited online to use the MiWaves JITAI for 30 days. Enrollment will occur in multiple waves, with the first two waves beta testing proposed trial procedures with small groups of  $n \approx 10$  participants and  $n \approx 20$ , and the final wave(s) involving a pilot trial with up to 150 EAs. Feasibility will be defined by the percentage of participants who consent to the study who ultimately download the MiWaves app.

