## **Measures**

Self-administered measures are reliable and valid among emerging adults. Please see Table 1 for more information about the domains queried at each assessment timepoint, the timeframes asked about for each domain at each timepoint, and references for the questions capturing each

domain. All the outcomes listed in Table 1 are exploratory, except for the bolded primary outcomes concerning feasibility and acceptability.

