**Table 1. Overview of MiWaves Measures, Assessment Timepoints, and Question Timeframes**

Domain	Assessment Timepoint					
	Screen	Baseline	Weekly	Daily	Post-Test	2M FU
Background Characteristics						
Demographics 	Current	Current				Current
Cell phone characteristics 	Current					
Substance Use Frequency, Quantity and Methods of Use						
Nicotine use 	1M	1M			1M	1M
Nicotine methods of use 		1M			1M	1M
Alcohol use QxF 	1M	1M		Yesterday	1M	1M
Alcohol TLFB 		7D	7D			7D
Cannabis use QxF 	1M	1M	7D	12h	1M	1M
Cannabis TLFB 		7D	7D			7D
Cannabis methods of use 			1M		1M	1M
Illicit drug use 			1M		1M	1M
Prescription drug misuse 			1M		1M	1M
Precursors of Cannabis Use						
Cannabis use motives 		Current		12h		Current
Cannabis cravings 		Current		Current		Current
Perceived risk of cannabis 		Current				Current
Social influences 		Current				Current
Mood/Affect 			7D	Current		
Stress 				Current		
Energy 				Current		
Readiness to Change Substance Use						
Importance rulers (nicotine, alcohol, cannabis) 	Current	Current			Current	Current
Likelihood and confidence rulers (cannabis) 		Current				Current
Substance Use Outcomes and Consequences						
Marijuana Adolescent Consequences Questionnaire 		1M			1M	1M
Young Adult Driving Questionnaire 		1M			1M	1M
DSM Symptoms Checklist 		1M			1M	1M
Protective Factors						
Protective Behavioral Strategies for Marijuana 		1M	7D		1M	1M
Social Support 		Current				Current
Behavioral Economic Measures						
Cannabis Purchase Task 		Current	Current			Current
Activity Level Questionnaire 		1M			1M	1M
Delayed Discounting Task 		Current	Current			Current
Brief Relative Reinforcement*			7D			
Mediators						
Social context of cannabis use 		7D	7D			7D

Domain	Assessment Timepoint					
	Screen	Baseline	Weekly	Daily	Post-Test	2M FU
Satisfaction with social events 				Current		
Distress 				Current		
Positive outlook 				Current		
Health Status, Outcomes and Service Utilization						

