Service Utilization 		Lifetime				2M
Mental Health						
Global Measure 		Current				Current
PHQ-2 		2W	7D		2W	2W
GAD-2 		2W	7D		2W	2W
ASI-3 		Current				
Mindfulness Attention Awareness Scale 		Current				Current
PCL-5 short form 		1M				1M
Physical Health						
Global Measure 		Current				Current
Pain Intensity 		7D				7D
Pain Interference 		7D				7D
Sleep Quality 		7D				7D
Sleep*				12h		
Exercise 				12h		
Acceptability and Feasibility (Primary Outcome Measures)						
Acceptability 105,*					Current	
Feasibility						

\*Items were created for this study

Notes: In the table above, 1M = Past Month, 2W = Past 2 weeks, 7D = Past 7 days, 12h = Past 12 hours.

Bolded items indicate Primary Outcome Measures. All other outcomes are exploratory.

Table cells which are blank indicate that the domain was not assessed at that timepoint.

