## 6. Human Use Considerations and Protections

This research is covered by a Certificate of Confidentiality from the NIH. All hired members of the research team will complete training and receive certification in Human Subjects Research Protection and HIPAA regulations, including Good Clinical Practice, and the investigators will keep current certifications up to date.

**Aim 1.** There will be no human subjects' involvement in Aim 1 of this proposal as it is focused on app and content refinement.

**Aim 2.** In this aim, we will conduct a pilot trial to test the feasibility and acceptability of a 2nd Generation just-in-time adaptive intervention (JITAI) with continually optimized population-based decision rules.

**Identifiable Information.** For each stage of the proposed research investigation, participants' names and contact information will be stored in a secure database, separate from their study data. Names will be linked to individual ID numbers *only* in a study database, which will be kept in a restricted access location only accessible to study staff. All study devices will be password protected, use UM encryption (e.g., Hub) whenever possible, and only accessed by study staff. UM encryption enables safeguards against data compromise, malware, and ransomware and has a user portal to manage devices in case of theft, loss, or forgotten passwords. All information collected will be accessible only to research staff who have completed and maintain mandatory training in the protection of human subjects and good clinical practices.

**Potential Risks.** Every effort will be made to ensure that study participants are protected from risks. Although it is not expected that there will be any risks to participants because of online assessment procedures, the risk of violation of confidentiality exists because human participants are giving personal information. Consent forms will contain a statement explaining mandatory reporting requirements for information regarding child abuse and intention to harm self or others, should this be disclosed in the context of the research, although we will not be collecting any assessment data on these topics.

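### The Objectives promise a test of preliminary efficacy that Aim 2, the outcome hierarchy, the analysis section and the described design do not support

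*Combined protocol and SAP*

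**What the plan says.** Section 2 (Objectives) says the study will "test the feasibility, acceptability, and preliminary efficacy of a person specific JITAI called MiWaves for reducing cannabis use". The other statements of purpose are narrower:

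- Section 3 (Project Aims), Aim 2: "Conduct a pilot trial to test the feasibility and acceptability of MiWaves, a 2nd generation MiSARA JITAI".
- Section 4 (Methods), Aim 2: "Conduct a pilot trial to test the feasibility and acceptability of MiWaves, a 2nd generation JITAI".
- Section 6, Aim 2: "we will conduct a pilot trial to test the feasibility and acceptability".

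The Measures section states: "All the outcomes listed in Table 1 are exploratory, except for the bolded primary outcomes concerning feasibility and acceptability". The notes to Table 1 repeat it: "Bolded items indicate Primary Outcome Measures. All other outcomes are exploratory". Cannabis use is therefore exploratory at every timepoint.

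On design, Section 4 says that participants "will be recruited online to use the MiWaves JITAI for 30 days". No control, waiting-list or assessment-only group is described. Under Pilot Trial, intervention messages may be sent twice a day, with reinforcement learning deciding whether and when. Neither randomisation nor delivery probabilities are stated. Section 5 plans frequencies and unspecified bivariate and multivariate exploration of trends.

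**The concern.** One stated objective has no estimand, contrast, model or limit on interpretation behind it. Cannabis use is measured repeatedly in people who all receive the app, so the natural analysis is change from baseline. A fall could then be reported as preliminary efficacy, with Section 2 as its warrant, and carried into the planning of the next trial. Nothing described in the plan would separate that fall from regression to the mean or from the effect of being assessed. The exploratory label limits how strongly a result may be claimed. It does not withdraw the objective, and it does not tell the reader that uncontrolled change is not evidence of efficacy.

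**Working it through.** **No figure to reproduce.** The pilot size of up to 150 comes without an effect size, standard deviation, alpha, power or precision target. The check is therefore mainly textual.

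**1. Contrasts available.** A between-group contrast needs a comparator, and none is described. A within-person message contrast needs known delivery probabilities, and none are stated. Micro-randomisation is mentioned only for the earlier SARA study (Sections 1 and 2). Before/after change is what remains.

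**2. Reasons for a fall with no effect.**
- Inclusion requires cannabis use three or more times each week over the past month, so entry selects on the behaviour later treated as an outcome.
- Baseline Assessment allows up to one month from screening consent to complete baseline and download the app, with no minimum gap. Table 1 asks the past-month cannabis item at both screening and baseline. Taking a month as 30 days, the windows share 30 − g days at a gap of g days: 30 on the same day, 23 at one week, 0 at 30 days. The 7-day "Cannabis TLFB" shares max(0, 7 − g) days with the screening window, so it is clear from one week on.
- Section 6, on potential benefits, says the assessments may themselves act as a very minimal intervention.

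**3. Direction.** For a normal measure selected above a cut-off c (in SD units) with test-retest correlation r, and with the selecting measure also serving as baseline:

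expected fall = (1 − r) × φ(c) / (1 − Φ(c)), in SD units.

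- c = −0.5, r = 0.9: 0.1 × 0.509 = 0.05
- c = 0, r = 0.8: 0.2 × 0.3989/0.5 = 0.2 × 0.798 = 0.16
- c = 1.0, r = 0.6: 0.4 × 1.525 = 0.61

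The fall is positive whenever r < 1. The values of c and r are assumptions.

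**4. Size in days per week.** This was simulated with zero effect. Assumptions:
- Each person has a Beta-distributed daily-use probability (concentration 1 or 2).
- Weekly deviations on the logit scale have autocorrelation 0.2, 0.5 or 0.8.
- Days per week are binomial out of 7.
- Entry requires either a four-week average of at least 3 days or at least 3 days in every week.
- Days stand in for the protocol's times of use.
- The app starts at baseline.

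Fall in the past-month item from a same-day baseline to post-test:

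| Assumed source-pool mean (days/week) | Weekly logit SD | Spurious fall (days/week) |
|---|---|---|
| 7 × 0.30 = 2.1 or 7 × 0.45 = 3.15 | 1.0 or 1.5 | 0.20 to 0.97 |
| 7 × 0.60 = 4.2 or 7 × 0.80 = 5.6 | 1.0 or 1.5 | 0.06 to 0.55 |
| 4.2 or 5.6 | 0.5 | 0.03 to 0.17 |

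Monte Carlo error is about 0.03 or less.

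Under the first row's inputs with baseline one week after screening, the 7-day measure (baseline to fourth weekly survey) gives 0.01 to 0.60, against 0.16 to 0.91 for the past-month item. It is the smaller of the two in every setting. With a same-day baseline it gives 0.20 to 1.08 and is smaller in only 19% of settings, so the measure helps only once its window clears the screening month.

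**The case against.** The strongest reply is that the document already contains its own limits. The efficacy wording occurs once, Aim 2 is confined to feasibility and acceptability in three places, all other outcomes are exploratory, and Section 5 plans no efficacy test. This stands as a limit on seriousness: the misreading is a risk in reporting, not a planned analysis. It does not remove the contradiction, because the objective is current text and nothing qualifies it.

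Some stronger readings are tempting, and the documents do not support them:

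- *Message delivery is not randomised.* The documents are silent. A reinforcement learning algorithm may assign messages with known probabilities, which would give a valid within-person contrast. All that can be said is that none is described.
- *The app features that can be switched on intermittently confound the efficacy claim.* Section 2 defines the JITAI as combining intervention and engagement strategies, and Pilot Trial calls these additional features of the app. They belong to the package, so they would complicate only a message-specific effect.
- *All assessment effects are external to MiWaves.* The twice-daily surveys sit inside the app. Assessment is only partly a rival explanation, chiefly through the baseline and weekly online surveys.
- *A false-positive rate can be quoted.* No paired test is planned, and such a rate would move with the same undocumented inputs as the table. Same-day baseline is also an extreme case: verification comes between screening and baseline, and activation follows the download. It is possible, but not shown to be typical.

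**Conclusion.** The point holds. Section 2 claims a property that the described design does not have. That conclusion rests on the text alone and is secure.

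That regression to the mean would push towards a fall is also well supported. It needs only that use varies over time and that the entry criterion excludes some people. Its size is not supported by the documents: about 0.03 to 1 day per week for the past-month item with a same-day baseline, depending on an assumed source population and week-to-week variability. It is smaller for the 7-day measure once baseline is at least a week after screening, but not necessarily zero. These figures show plausibility and do not predict what this trial will see.

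A reader might infer that the trial is invalid or that its main results are biased. Neither follows: the primary feasibility and acceptability outcomes do not depend on a cannabis-use contrast. The defect is one of stated purpose and interpretation, worth correcting because the correction is nearly free.

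**What to change.** 1. **Section 2.** Delete the words preliminary efficacy, or limit them to a randomised message contrast if one exists.
2. **Section 5.** Add a sentence that before/after change in cannabis use is uncontrolled description and does not establish efficacy.
3. **Pilot Trial and Section 5.** State whether the algorithm randomises message delivery. If it does, log the delivery probability at each decision point and use those probabilities in any exploratory estimate of message effects. Pilot Trial already names message effort as a possible moderator of such effects. If it does not, report message associations as descriptive only.

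Settle the third item before the pilot wave, since probabilities not logged at the time may be unrecoverable.

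No particular cannabis measure, subgroup or model needs to be imposed on an exploratory outcome. The cost is weaker efficacy wording and, if delivery is randomised, a small logging task. No new data collection from participants is needed.

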## 3. Project Aims

The **specific aims** of this project are to:

**Aim 1: Refine the MiSARA JITAI to reduce cannabis use among EAs.**

**Aim 2: Conduct a pilot trial to test the feasibility and acceptability of MiWaves, a 2nd generation MiSARA JITAI with continually optimized population-based decision rules.**

The achievement of the proposed aims addresses a significant public health problem, namely the increases in cannabis use among EAs. The innovation is grounded in the development of a real-time, real-world, personalized, and scalable intervention approach to reduce substance use among EAs. This work is highly innovative since, despite promising results, evidence based JITAIs for cannabis use among EAs are lacking. Reducing cannabis and other drug use among EAs could have a major public health impact by preventing adverse health consequences (e.g., injury), development of SUD, and associated risky behaviors (i.e., drugged driving).

